#### CONFIDENTIAL

This material is the property of the NYU School of Medicine and Langone Medical Center. Do not disclose or use except as authorized in writing by the study sponsor

Use of continuous glucose monitoring system with intensive feedback in adolescents with poorly controlled type 1 diabetes  
Version Date: 04/26/2018

appointments and staff will determine if they are interested in participation in the study using a recruitment script uploaded under recruitment materials section.

The study is minimal risk (MR). The device is approved by the FDA and is being used according to its cleared/approved labeling. The probability and magnitude of harm or discomfort anticipated in this research is similar to those ordinarily encountered in daily life or during the performance of routine physical or psychological examinations or tests.

The use of the CGMS will be described.

The study will consist of 4 phases.

1: For all participants at entry into the study the participant's HbA1c will be measured in the lab at the location of the patient's visit and his/her glucose meter will be downloaded as part of routine care. The average capillary glucose level, (with range and standard deviation) and the average number of tests per day over the prior 14 days will be recorded. The current individual care plans for self-management of type 1 diabetes will be reviewed by the study personnel with the participant.

Questionnaires will be administered to all the participants except Appendix F:

- 1) Appendix A - Stages of Change measure (original). We created a 5 item questionnaire to assess the patient's current stage.
- 2) Appendix B - Psychosocial self-efficacy (University of Michigan Diabetes Research and Training Diabetes Empowerment Scale short-form) - DES. 8 items. Also available for use.(3-6)
- 3) Appendix C - Knowledge and risk perception (University of Michigan Diabetes Research Training Center Diabetes Knowledge Scale). 23 items - DKT. We are substituting rapid acting insulin for NPH insulin in item 17 since NPH is not used in our study population. Available for use without permission as long as the source is quoted.(7, 8)
- 4) Appendix D - Quality of life (Peds QL 3.2, Diabetes module,) – Peds QL. 33 items on a Likert scale.(9)

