## Remove transmitter latch

The use of the CGMS (Dex-COM ®) device will be explained and the device placed on the subject's abdomen by a trained study personnel. The participant will be instructed to continue to perform capillary glucose testing as usual at home, and to calibrate the Dex-COM ® at least twice daily. The participant will be encouraged to review the CGMS readings as often as possible, particularly before meals, bedtime, and 1-2 hours after eating. If the glucose result on the CGMS is  $\geq 300$  mg/dl, or  $\leq 80$  mg/dl, he/she will be instructed to verify the results by using the glucose meter, follow the usual care instructions and then call the Pediatric Diabetes team for advice. An alarm upper limit will be set on the CGMS device at 300 mg/dl, and a lower limit at 80 mg/dl. He/she and the investigator will agree on a time of day for daily phone contact. The phone advice will be based on standard medical management of type 1 diabetes mellitus, focusing on details of insulin dosing, carbohydrate counting, and exercise. A tally will be kept of the number of daily phone calls completed with the medical staff and the participant. The parent will be able to speak to the medical staff during phone calls, but the primary contact will be with the adolescent participant.

2: Study visit # 2 will be in 1 week from the initial visit for both the study and control groups. The patients in the study group will return the CGMS device at the time of the 1 week appointment. The glucose meters of all participants will be downloaded, and the data will be extracted as above. The Empowerment Scale short form and the measure of Stages of Change will be administered to both groups. A brief questionnaire about the participant's response to use of CGMS will be given to the study group (CGM Satisfaction scale – Appendix F). Study and control groups will both be given a \$50

CONFIDENTIAL

This material is the property of the NYU School of Medicine and Langone Medical Center. Do not disclose or use except as authorized in writing by the study sponsor

Use of continuous glucose monitoring system with intensive feedback in adolescents with poorly controlled type 1 diabetes  
Version Date: 04/26/2018

reimbursement for time and travel.

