#### ANALYSIS:

Measures of the level of glycemic control will be assessed primarily by HbA1c and secondarily by the average glucose tests results on the patient's glucose meter. Comparison of the glucose results (average, range, standard deviation, number of daily tests) between the study entry, 1 week, 1 month and 3 month follow up visits will be done. Comparison of HbA1c at entry and at 3-month follow-up will be performed. Questionnaire scores will be compared between study entry, 1 week follow up, 1 month follow up and 3-month follow-up visits for DES and Stages of Change scales. We will determine if there is a correlation between the scores on the questionnaires and measures of glucose control. We will classify study and control participants into adherent and non-adherent groups.

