#### CONFIDENTIAL

This material is the property of the NYU School of Medicine and Langone Medical Center. Do not disclose or use except as authorized in writing by the study sponsor

Use of continuous glucose monitoring system with intensive feedback in adolescents with poorly controlled type 1 diabetes  
Version Date: 04/26/2018

Dichotomizing participants into adherent and non-adherent:

Study subjects will receive points for calibrating the CGM device and for successfully completing phone contact with the pediatric diabetes team. The patient will receive 2 points for calibrating the device 2 times/day for at least 5 days, 1 point for calibrating the device 2 times on at least 3 days and 0 points for calibrating any less. Similarly the patient will receive 2 points for completing successful phone contact with study personnel for at least 5 days, 1 point for completing phone contact on at least 3 days and 0 point for contact any less than mentioned before. The two scores will be added to get a total score. Patients with scores 3-4 will be classified as adherent and scores 0-2 will be classified as non-adherent. Control subjects who complete 4 or more phone calls on different days will be classified as adherent and those who complete fewer phone calls will be classified as non-adherent.

Statistical methods:

Demographic data will be tabulated. Statistical analysis of questionnaires will be done according to published standards. The paired t-test will be used for comparisons involving stages of change score.

Independent variables will include the empowerment score, average glucoses, HbA1c and whether the subjects fall into the adherent vs. non-adherent groups. Dependent variables include glucose level(s) and stage of change. We will analyze the 7 day average glucose by meter download and categorize the results in terms of change: No change (-15 to + 15), Higher ( $\geq + 15$ ) or Lower ( $\leq -15$ ). We will analyze the HbA1c and categorize the results in terms of change: No change ( $> -0.5$  to  $+ 0.5$ ), Higher ( $\geq + 0.5$ ) or Lower ( $\leq -0.5$ ). Stages of change (Appendix A) will be categorized as unchanged, improved or worsened. In addition, descriptive statistics including quality of life, diabetes knowledge scale, and demographic variables will be tabulated.

Statistical Analysis for sensor study:

Questionnaires:

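### The range of meter glucose is compared between visits although it widens with the number of readings, so a change in range cannot be read as a change in glycaemic variability

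*Combined protocol and SAP*

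**What the plan says.** The ANALYSIS section lists four meter summaries for comparison across visits: "Comparison of the glucose results (average, range, standard deviation, number of daily tests) between the study entry, 1 week, 1 month and 3 month" follow-up. It ranks glycaemic control as "assessed primarily by HbA1c and secondarily by the average glucose tests results on the patient's glucose meter", and gives range no rank.

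METHODS, phase 1, sets the extraction at entry: "The average capillary glucose level, (with range and standard deviation) and the average number of tests per day over the prior 14 days". At the 1-week visit "The glucose meters of all participants will be downloaded, and the data will be extracted as above", and the 1-month and 3-month visits repeat this. Statistical methods introduces a different window, for the average only: "We will analyze the 7 day average glucose by meter download".

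In the wear week, CGM participants are told to go on with their usual meter testing and to calibrate "at least twice daily. The participant will be encouraged to review the CGMS readings as often as possible". When the sensor shows 300 mg/dl or more, or 80 mg/dl or less, "he/she will be instructed to verify the results by using the glucose meter". Controls have neither task.

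The plan does not fix the number of readings behind a range, adjust for it, or use a spread measure based on quantiles.

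**The concern.** Taken as the distance between the highest and lowest reading, a range can only stay the same or grow as readings are added to a set. Across separate windows, its expected value rises with the count. The plan compares the count itself as an outcome, and the trial's aim is to affect motivation or behaviour, so the count may well differ between visits and between arms. A shift in testing habits alone could then produce a shift in range that looks like a change in variability. The SD in the same list is almost free of this dependence. At stake is the interpretation of one unranked glucose summary, not of the main result.

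**Working it through.** The documents give no SD, expected range, test or alpha for this comparison, so there is no planned figure to reproduce. The check holds the glucose distribution fixed and changes only the number of readings.

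**Inputs from the documents.** A 14-day look-back (METHODS, phase 1); 40 CGM and 20 control participants (SUBJECTS); 4-8 tests a day as the usual frequency (background text).

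**Assumptions.** Independent readings; mean 220 mg/dl; within-person SD 80 or 90 mg/dl; a change from 2 to 4 tests a day; two-sided 5% tests.

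**Step 1: number of readings.** 14 × 2 = 28 and 14 × 4 = 56.

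**Step 2: expected range, normal readings.** E[range] = d2(n) × SD, where d2(n) = ∫{1 − F(x)^n − [1 − F(x)]^n}dx and F is the standard normal distribution function. This gives d2(28) = 4.03 and d2(56) = 4.59. The ratio is 4.586 / 4.027 = 1.139, or +14% whatever the SD. For SDs of 60, 80 and 100 mg/dl the expected range goes from 242 to 275, 322 to 367 and 403 to 459 mg/dl. From 4 to 8 tests a day, d2(112) / d2(56) = 5.096 / 4.586, or +11%.

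**Step 3: simulation with other shapes and meter limits, 28 to 56 readings.**

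| Assumed readings | Mean range (mg/dl) | Change | Mean SD (mg/dl) |
|---|---|---|---|
| Normal, SD 90, limited to 30-600 | 348 → 387 | +11% | 87.7 → 88.3 |
| Lognormal, SD 90, limited to 30-600 | 359 → 414 | +15% | 87.4 → 88.0 |
| Lognormal, SD 80, limited to 20-600 | 322 → 372 | +16% | 78.3 → 78.8 |
| Lognormal, SD 80, limited to 40-400 | 280 → 302 | +8% | 73.4 → 73.7 |

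Without limits, the lognormal SD 80 case goes from 324 to 377 (+16%) and its SD from 78.5 to 79.3 (+1%).

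**Step 4: false signals with unchanged glucose (lognormal, SD 80, no limits).** If all 40 CGM participants went from 2 to 4 tests a day, a paired t-test would reject in about 83% of runs for range and about 6% for SD. If only the CGM arm tested more, a 40 v 20 comparison of the changes in range would reject in about 40%. For 3 to 5 tests a day, the range figures are 53% and 21%. For a single participant going from 2 to 4 a day, range rises with probability 0.70 and SD with 0.53.

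**Step 5: meter limits do not remove the false signal.** With values limited to 40-400, the mean shift is 302 − 280 = 22 and the SD of the difference is √(31² + 19²) = 36, a ratio of 0.6. Without limits the ratio is 53.9 / 115.0 = 0.47. The widening is smaller but no harder to detect.

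**Step 6: would the share of readings at or beyond 80 and 300 mg/dl be safer?** Under a normal distribution with mean 220 and SD 90, about 6% of routine readings are at or below 80 and about 19% at or above 300, about 25% in all. That is 6.9 of 28 readings. One confirmed triggered check a day for 7 days (assumed) gives (6.9 + 7) / 35 = 40%, with glucose unchanged. The same checks raise the SD from about 89 to about 103 mg/dl.

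**Step 7: which visits are affected.** The device is returned at 1 week. A 14-day look-back from a 1-month visit at day 28-30 starts at day 14-16, after the wear week. It also starts no earlier than the end of the second sensor week that the CONSENT section mentions.

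**The case against.** The strongest reply is that range decides nothing here. HbA1c is primary and the meter average secondary. The change categories in Statistical methods cover average glucose, HbA1c and stage of change, but not range. No test, direction or sample size depends on it. Elsewhere the plan uses range, mean and SD as a routine descriptive set, so range may be meant descriptively here too. Because SD and number of tests are compared alongside it, a wider range with more tests and a steady SD would be visible to a careful reader. All of this stands, and it makes the point minor. It does not remove it: the text calls for a comparison of range between visits and does not say to read it against the count.

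Three stronger readings are tempting, and the documents do not support them.

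- A reader might infer that better testing would be reported as glycaemic harm. The plan never says how a wider range will be interpreted.
- A reader might infer that any participant who tests more will look more variable. The widening is in expectation; for one person going from 2 to 4 tests a day it occurs about 70% of the time.
- A reader might take 7 days as the window, where 14 to 28 readings give +16% to +20% with SD 90 (299 to 348, or 298 to 359 mg/dl). The stated extraction window is 14 days; the 7-day figure belongs to the average.

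It is also fair that no doubling of testing is planned, and that CGM users are told to keep to their usual meter testing. The calibration and verification checks can add readings in the wear week only.

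**Conclusion.** The point holds as a minor one. A between-visit change in the range of meter glucose cannot be read as a change in glycaemic variability unless the number of readings is the same. Over 14 days, an assumed change from 2 to 4 tests a day widens the expected range by about 11% to 15% in most of the cases tried (16% in the lognormal SD 80 cases, about 8% with values limited to 40-400 mg/dl). The SD moves by about 1% or less. The percentages rest on independent readings, an unchanged distribution and the assumed change in frequency; actual reading counts are not known from the documents.

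The advantage of the SD has a limit. Where extra readings are triggered by high or low sensor values, as in the CGM arm during the wear week, the SD and the average can shift as well. That is a separate sampling bias. It makes the 1-week meter variability in that arm uncertain whichever spread measure is used. The primary HbA1c comparison is not affected.

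**What to change.** - In ANALYSIS, name the SD (or SD divided by the mean) as the meter-based variability measure compared between visits.
- Keep range in descriptive tables only, with the number of readings beside it.
- State one look-back window for these summaries. The 14-day extraction and the 7-day average are not reconciled, and at 4 tests a day a 7-day window alone narrows the expected range by 12% (4.027 / 4.586 = 0.878). A 14-day window at the 1-week visit also reaches back before study entry.
- Do not substitute the percentage of meter readings at or below 80 and at or above 300 mg/dl at the 1-week visit.
- Say that 1-week meter variability in the CGM arm will be interpreted with caution, and rely on the 1-month and 3-month comparisons.

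The cost is a few lines of analysis wording and a recalculation from downloads already planned. No visit or procedure is added.

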#### SUBJECTS:

Sixty adolescents, ages 13-22 years, with type 1 diabetes and an HbA1c  $\geq 8\%$  who are also naive to CGMS or who have not used a CGMS in at least six months use will be recruited from the diabetes outpatient population followed at Bellevue Hospital, Lutheran Hospital, Woodhull Hospital, and the NYU Fink Pediatric Ambulatory Care Center. Forty subjects will be randomly assigned to the CGMS group and 20 subjects will be assigned to the control group.

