Daily Phone Log: (Appendix H): Scoring will be done for each day of the initial week of the study, in both CGM intervention group, and control group based on the following: Study subjects will receive points for calibrating the CGM device and for successfully completing phone contact with the pediatric diabetes team. The patient will receive 2 points for calibrating the device 2 times/day for at least 5 days, 1 point for calibrating the device 2 times on at least 3 days and 0 points for calibrating any less. Similarly the patient will receive 2 points for completing successful phone contact with study personnel for at least 5 days, 1 point for completing phone contact on at least 3 days and 0 point for contact any less than mentioned before. The two scores will be added to get a total score. Patients with scores 3-4 will be classified as adherent and scores 0-2 will be classified as non-adherent. Control subjects who complete 4 or more phone calls on different days will be classified as adherent and those who complete fewer phone calls will be classified as non-adherent.

The distribution of the data will be assessed using the Kolmogorov-Smirnov test. All categorical variables will be presented as mean +standard deviation. For categorical variables the differences between the compliant and non-compliant groups will be assessed using the Mann Whitney or rank order Wilcoxon test based on normality. For categorical variables independent sample t test will be used. Univariate analysis will be used to establish correlation between variables of interest.

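### DES, Stages of Change and meter glucose are each recorded at four visits, but their association is to be tested by a univariate correlation with no participant term and no stated visit or unit of analysis

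*Combined protocol and SAP*

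**What the plan says.** SUBJECTS sets the sample: "Sixty adolescents, ages 13-22 years, with type 1 diabetes", and "Forty subjects will be randomly assigned to the CGMS group and 20 subjects will be assigned to the control group". The unit of randomisation is therefore the participant.

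METHODS describes four study phases. DES, Stages of Change and a meter download occur at entry, 1 week, 1 month and 3 months. ANALYSIS confirms this for the meter results ("between the study entry, 1 week, 1 month and 3 month follow up visits will be done") and for the two scales ("1 month follow up and 3-month follow-up visits for DES and Stages of Change scales"). HbA1c is taken twice: "Comparison of HbA1c at entry and at 3-month follow-up will be performed".

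The association question is in ANALYSIS: "We will determine if there is a correlation between the scores on the questionnaires and measures of glucose control". The method is in the last paragraph of the statistical section, after the Daily Phone Log scoring: "Univariate analysis will be used to establish correlation between variables of interest". Nothing else is said about this analysis. The paired t-test under Statistical methods is for comparisons of the stages of change score, not for the association. The change categories in the same section cover meter glucose, HbA1c and stage. None is defined for DES, and none is linked to the correlation.

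**The concern.** With four linked score-glucose pairs per person, an ordinary correlation must either use all pairs or choose among them. Using all of them treats repeated records from one adolescent as if they came from different adolescents, and the standard error is then too small. Using one visit at a time avoids that, but it only shows whether people with higher scores have lower glucose.

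The AIM asks whether short-term monitoring with feedback affects motivation or behaviour. The hypothesis has feedback and self-efficacy influencing stage of change and possibly glucose. These statements concern movement within a participant. The correlation is the plan's link between the psychological measures and glycaemia. As specified, it does not separate change within a person from stable differences between people, and the choice of visits could be made after the data are seen.

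**Working it through.** **Inputs from the documents.** 60 participants (40 + 20) and m = 4 visits for DES, Stages of Change and meter glucose, so up to 60 × 4 = 240 pairs. The documents give no alpha, power, effect size, standard deviation or dropout for the 60, so there is no planned figure to reproduce.

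**Assumed, not in the documents.** Two-sided 5%; exchangeable visits; the same ICC for score and glucose, from 0.3 to 0.8; complete data; for power, a within-person correlation of size 0.3.

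**1. Visits pooled, no true association.** The variance of the correlation is inflated by 1 + (m − 1) × ICC × ICC = 1 + 3 × ICC². The true error is 2 × [1 − Φ(1.96 / √inflation)].

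| ICC | Inflation | Effective records (240 / inflation) | True error, formula | True error, simulated |
|---|---|---|---|---|
| 0.3 | 1.27 | 189 | 8.2% | 8.0% |
| 0.5 | 1.75 | 137 | 13.8% | 13.9% |
| 0.7 | 2.47 | 97 | 21.2% | 21.5% |
| 0.8 | 2.92 | 82 | 25.1% | 25.0% |

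The simulation used 10,000 runs per setting. A separate run of 20,000 gave 8.2%, 13.8%, 21.2% and 25.7%.

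**2. One visit, one record per person.** Simulated error stays near 5%. The correlation seen at a single visit is ICC × r_between + (1 − ICC) × r_within. By Fisher's z, power is approximately Φ(atanh(r) × √(60 − 3) − 1.96), plus a negligible opposite tail.

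- r_between = 0, ICC 0.5: r = 0.5 × 0.3 = 0.15, 0.1511 × 7.55 = 1.14, power about 21%.
- r_between = 0, ICC 0.7: r = 0.3 × 0.3 = 0.09, 0.0902 × 7.55 = 0.68, power about 10% to 11% (simulated 10.8%).
- r_between = 0.3, any ICC: r = 0.30, 0.3095 × 7.55 = 2.34, power about 65%.

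With r_between = 0, simulated power runs from 37% at ICC 0.3 to 7% at ICC 0.8.

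**3. One change-on-change pair per participant (entry to 3 months).** Differencing removes the stable person component, so the correlation of changes equals r_within = 0.3 with n = 60. Power is again about 65% (simulated 65% to 66%), with simulated error of 4.7% to 5.4%.

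**4. All four visits with a participant term.** Residual degrees of freedom are 60 × 3 − 1 = 179. Power is approximately Φ(0.3095 × √178 − 1.96) = Φ(4.13 − 1.96) = 98.5%, and simulation agrees. Simulated error is 4.8% to 5.4%. Adding visit and arm-by-visit terms costs 3 + 3 degrees of freedom, leaving 173; Φ(0.3095 × √172 − 1.96) = Φ(4.06 − 1.96), about 98%.

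**The case against.** The strongest reply is that this is a gap in wording rather than a demonstrated error, and much of that stands.

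- A reader might infer that the plan pools 240 records. No section says so. The inflated error applies only if an analyst makes that choice; the point is that nothing prevents it.
- A reader might infer that a visit-by-visit correlation is wrong. It is not. Each such test holds 5% and answers a legitimate between-person question. Running four of them raises multiplicity, which is a separate matter.
- A reader might infer that no sound reading exists. Correlating one change in score with one change in glucose per participant is sound, and the plan already classifies some changes. However, it does not connect those categories to the correlation, has none for DES, and words the question in terms of scores and measures of control rather than changes.
- The low single-visit power is a worst case: it requires no between-person association. With a between-person correlation of 0.3 the figure is about 65%.
- A reader might extend the four-visit figures to every questionnaire or to HbA1c. PedsQL is taken at three visits, PHQ-2 and HbA1c at two, and the knowledge test and the satisfaction scale once. HbA1c is the primary glycaemic measure, so the figures cover two scales against the secondary one.
- Exchangeability is a simplification. Entry meter data cover the prior 14 days. If that window is kept at 1 week, about half the days at the second visit repeat those at entry. Statistical methods also mentions a 7-day average, which would reduce the overlap.

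What remains is that the only named method makes no use of the repeated structure, and that a better method is available on data already being collected.

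**Conclusion.** The point holds as a cheap improvement to a secondary analysis. For DES and Stages of Change against meter average glucose, the plan names a univariate correlation and leaves the visits and unit of analysis open. If visits are pooled, a nominal 5% becomes about 8% to 26%. If single visits are used, the test is valid but does not address within-person change, with power of about 21% or 11% (ICC 0.5 or 0.7) when there is no between-person link and about 65% when the between-person correlation is 0.3. Change-on-change would be sound at about 65% power but is not specified. A model with a participant term reaches about 98%. The documents do not support saying that the plan will produce inflated error, only that it permits it. All error and power figures rest on the assumed ICCs, the assumed correlation and complete data.

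**What to change.** In the final paragraph of the statistical section, replace the univariate correlation for DES and for the numeric Stages of Change score against meter average glucose. Use one linear mixed model per score: meter average glucose at each visit as outcome, a participant random intercept, visit and arm as fixed effects, and the score entered as two terms, the participant's mean and the visit's deviation from it. Report the deviation (within-person) and mean (between-person) coefficients separately. Report the model with and without arm-by-visit, because that term removes co-movement of score and glucose caused by the intervention.

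For HbA1c, and for scores taken at entry and 3 months, relate change to change with one pair per participant. Where the Stages of Change category is the outcome, use an ordinal model with a participant effect, or the per-participant change category. State that visits will not be pooled in a simple correlation.

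The cost is SAP wording and slightly more analysis work, with no new data or participants. The result is a regression coefficient rather than a single correlation, and p-values will be larger than under pooling when the association is only between people.
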